5. Screening for Eligibility: Subjects who provide written informed consent will undergo a screening for eligibility by the study physician using the Medical History and Physical Exam form. The inclusion and exclusion criteria are based on the study design and health suitability to undergo exercise training, supplementation, blood draws, biopsy, CT scan, and vaccination. If exclusion criteria are temporary, recruits may participate in the study (or specific procedure related to criteria) once condition is no longer exclusionary. The criteria and method for collection of this information are listed:

a. Inclusion Criteria: information collected from subject self-report

- (1) Veteran
- (2) Age 60-80 years
- (3) Body Mass Index of 18.5 - 29.9 kg/m²

b. Exclusion Criteria: information collected from subject self-report

- (1) Currently participating in any other research study involving an intervention
- (2) Smokes tobacco products (subject word to halt smoking is also sufficient)
- (3) Tetanus or TDAP vaccine in previous two years
- (4) Allergic to vaccination
- (5) Seizure in past 3 months
- (6) Guillain-Barre Syndrome in past 3 months
- (7) Takes the medications heparin, plavix / clopidigrel, or coumadin / warfarin
- (8) Allergic to lidocaine
- (9) Significant problem with fainting
- (10) Problems walking or exercising with both legs
- (11) Participated in a weight-lifting program targeting the thighs in last 3 months
- (12) Pains, tightness or pressure in chest during physical activity such as walking, climbing stairs, household chores, or similar activities

c. Absolute Exclusion Criteria: information collected from CPRS review and/or subject self-report. The medical history will include a discussion between the subject and the study physician of the exclusion criteria that may have been reviewed during the pre-screening of the CPRS Problem List. The physician will assess the available information and document whether or not the subject is excluded.

- (1) Enrolled in another interventional study (CPRS Category II Flag)
- (2) Metastatic cancer or undergoing chemotherapy
- (3) Cerebral aneurysm or intracranial bleed in past year
- (4) End-stage congestive heart failure (NYHA Stage IV)
- (5) Unstable abdominal or thoracic aortic aneurysm (>4cm)
- (6) Renal disease requiring dialysis
- (7) Allergic to lidocaine or vaccination
- (8) Acute retinal hemorrhage or ophthalmologic surgery in past 3 months

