- (9) Bone fractures in the pelvis, legs, or feet in the last 3 months
- (10) Hernia that causes pain during physical activity
- (11) Myocardial infarction or cardiac surgery in past 3 months
- (12) Pulmonary embolism or deep venous thrombosis in past 3 months
- (13) Proliferative diabetic retinopathy or severe nonproliferative retinopathy
- (14) Active suicidality or suicidal ideation
- (15) Systemic bacterial infection
- (16) Taking heparin, plavix / clopidigrel, or coumadin / warfarin
- (17) Taking ASA (in any form) and unable/unwilling to discontinue at least 10 days prior to muscle biopsy
- (18) Unwilling to halt concurrent use of amino acid or protein supplements
- (19) Unwilling to halt new use of nutritional supplements
- (20) Unwilling to maintain current normal diet
- (21) Guillain-Barre Syndrome in past 3 months
- (22) Tetanus vaccination in past 2 years
- (23) History of allergic reaction to vaccination
- (24) Encephalopathy in past 7 days
- (25) Active oral or genital herpes
- (26) Current use of appetite stimulants
- (27) Significant history of seizures or seizures in past 3 months
- (28) Current treatment for mania or bipolar disorder or taking lithium.

d. **Potential Exclusion Criteria: evidence for potential exclusion criteria will be collected from CPRS review and/or subject self-report.** *Certain issues may also be assessed by the physical exam.

- (1) Diagnosis of a cognitive deficit
- (2) Untreated severe aortic stenosis: if there is evidence in CPRS Problem List or subject self-report of untreated aortic stenosis, then physician judgment for inclusion must be

based on an available echocardiogram, or evidence a valve area of $< 1\text{cm}^2$, or a history in the past 3 months of syncope, heart failure, or angina.

- (3) *Uncontrolled diabetes mellitus (HbA1C>10)
- (4) *Uncontrolled hypertension or hypotension ($>160/100$, <100 systolic)
- (5) *Uncontrolled malignant cardiac arrhythmia (sustained ventricular tachycardia > 3 beats, complete heart block, atrial flutter, symptomatic bradycardia)
- (6) Unstable angina (at rest or increased pattern in past month)
- (7) Allergic to latex or tape
- (8) Bleeding or clotting disorders, family history of bleeding disorders, problems with abnormal bleeding
- (9) Taking any non-ASA NSAID and unable or unwilling to discontinue use for 3 days prior to the muscle biopsy procedure

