- (10) Taking Fish Oil, Gingko, Garlic, Saw Palmetto, Turmeric, or Vitamin E and unable or unwilling to discontinue use for 10 days prior to the muscle biopsy procedure. Multivitamin containing vitamin E is acceptable and does not need to be halted.
- (11) Significant history of fainting
- (12) Significant problems with chronic pain
- (13) Uncontrolled asthma or allergies
- (14) Taking lactulose, nitrates plus hypertension medications or Viagra
- (15) Liver cirrhosis or other severe liver disease
- (16) History of peripheral artery disease
- (17) Steroid or androgen use in past 3 months that physician feels may confound study
- (18) Other physician judgment

e. **Other Exclusion Criteria: information collected during the physical exam by the study physician or qualified designee.** Blood will be drawn (less than or equal to 60ml or 2 ounces) for lab analyses by the hospital clinical lab at study entry, after completion of the exercise training program, and upon completion of the study for tests related to eligibility, safety, and research data.

- (1) Blood Pressure greater than 160/100 or <100 systolic.
- (2) HbA1C>10
- (3) CBC or PT/PTT/INR results that the study physician determines indicate a risk for excessive bleeding.
- (4) Clinical labs performed for safety monitoring including AST, ALT, creatinine, and BUN
- (5) Other tests that performed to measure immune function include HbA1C, CBC, CRP, ESR, cholesterol HDL and LDL, and blood differential.

f. **Exclusion Criteria Based on Other Physician Judgments:** older veteran subjects often possess numerous comorbidities that result in a complex and unique set of health issues. Thus, in addition to the specific exclusion criteria named above, the physician must also use a considerable amount of judgment in determining whether a recruit should be excluded even though the recruit meets the named inclusion criteria and does not meet the named exclusion

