9. **Vaccination:** The International Society of Exercise and Immunology considers response to vaccination the gold-standard for assessment of immune function in the context of exercise [38]. Multiple vaccine options were considered for use in the proposed study. Vaccination with antigen more likely to be naïve to subjects is preferable. However, the risk to benefit ratio of using the keyhole limpet protein or the herpes zoster live-attenuated virus was considered unacceptable. The influenza vaccine was considered since the epitope may change yearly, but this option could limit recruitment outside of flu season by availability of the vaccine and during flu season by availability of unvaccinated veterans. The tetanus, diphtheria, and pertussis (TDAP) vaccine has the advantages of benefit to the subject, low risk, low cost, and available test kits to measure response.

a. **Procedure:** The vaccine will be administered by a study physician to each subject after 2-weeks of supplementation. Blood will be collected at baseline and 1 and 2-weeks post-immunization to determine the effects of the supplement on the humoral response. Two time-points were chosen in case the response is delayed in older adults relative to the response in

younger adults [48]. If needed to accommodate scheduling, the supplementation period may be extended. The vaccination and second biopsy may occur up to 5 days late and the two post-vaccination blood draws may be delayed by one day if necessary.

For each study procedure a qualified study staff member will perform the procedure, i.e. a study physician will administer the vaccine and the study coordinator will draw blood. However, non-study staff such as the GRECC nurse or a CAVHS phlebotomist may also be utilized as needed, without being added as study staff, if the activity falls within their CAVHS job duties.

- b. **Benefit:** The TDAP vaccine was chosen because of the direct benefit it will provide to older subjects [49]. Tetanus, for example, is uncommon in the United States, but 70% of cases involve older adults and individuals over 60 years of age experience greater than a 50% mortality rate [50;51]. However, problems with these diseases are avoidable because the vaccine is safe for use in older adults.

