- c. **Risk:** The most common problems in adults are mild or moderate: pain at injection site (mild 2 in 3, moderate 1 in 100); redness or swelling at site (mild 1 in 5, moderate 1 in 25, severe 3 in 100); fever (mild 1 in 100, higher 1 in 250); headache (mild 3 in 10, moderate 1 in 300); tiredness (mild 1 in 4), and nausea, vomiting, diarrhea, or stomach ache (mild 1 in 10, moderate 1 in 100). Chills, body aches, sore joints, rash, or swollen glands are uncommon. A severe allergic reaction could occur after any vaccine (rare, less than once in a million doses). Individuals who are allergic or have experienced unexplained problems (coma, seizures) after vaccination, or has had Guillain-Barre Syndrome should not be vaccinated.
- d. **Minimization of risk:** The most common problems can be safely managed with symptomatic treatment. Individuals who should not be vaccinated will be excluded. The procedure will be postponed until recovery for subjects with mild illness or fever. All subjects will be informed of the risks and advised to call the study physician or staff immediately should a severe reaction occur.

10. Resistance Exercise Training Program: The study will use a resistance exercise routine that we have previously used to elicit cellular and molecular responses in muscle associated with immune function and to improve muscle mass and strength of the thigh for older adults [2;3;40;52].

- a. **Procedure:** The resistance exercise program will use three exercises to strengthen the thigh muscles including bilateral knee extension, knee curl, and leg press. Exercises are completed on air-driven exercise equipment in a seated position. Exercise sessions are always supervised by a study team member.
- b. **Strength Testing:** Strength will be determined using the 1-repetition maximum test [52]. A brief warm-up period will include approximately 10 minutes of mild aerobic activity followed by approximately 6 repetitions of lifting warm up at for a resistance exercise at a "somewhat heavy" load. The load is then gradually (~5-10%) increased such that the maximum capability for lifting is reached in approximately 10 total repetitions. Subjects will rest 60 seconds between repetitions after the warm up. Subjects rest five minutes prior to the next test completed in the order of press, curl, and extension.

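### The Guillain-Barre exclusion reaches back only 3 months, although the vaccine risk text bars anyone with a history and promises to exclude them

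*Combined protocol and SAP*

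**What the plan says.** The relevant text is in section 5 (Screening for Eligibility) and in the Vaccination section. The protocol numbers two sections 9; the Vaccination section is the second of them.

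- **Vaccination, 9.a:** "The vaccine will be administered by a study physician to each subject after 2-weeks of supplementation". Vaccination is part of the schedule for all participants.
- **Vaccination, 9.c (Risk):** a person who "has had Guillain-Barre Syndrome should not be vaccinated". No look-back period is given.
- **Vaccination, 9.d (Minimization of risk):** "Individuals who should not be vaccinated will be excluded".
- **Section 5.b(6), self-report list, and section 5.c(21), absolute exclusions:** both read "Guillain-Barre Syndrome in past 3 months".
- **Section 5, opening paragraph:** "If exclusion criteria are temporary, recruits may participate in the study (or specific procedure related to criteria) once condition is no longer exclusionary".
- **Section 5.f:** beyond the named criteria, "the physician must also use a considerable amount of judgment in determining whether a recruit should be excluded". Section 5.d(18) also lists other physician judgment as a potential exclusion.

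**The concern.** The risk text and the criteria meant to put it into effect define different groups. Sections 9.c and 9.d together bar anyone with a history of Guillain-Barre Syndrome. The criteria bar only those with an episode in the last 3 months. People with an older episode fall in the gap: they satisfy the lists, enter the trial and are scheduled for a vaccine that the protocol says they should not have.

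What is at stake is participant safety and whether a stated commitment is kept. No endpoint, sample size or error rate is affected. The gap matters because the lists guide what recruits are asked and what is looked for in the record. If the listed item asks about 3 months only, a recruit can answer it truthfully and the older episode need never be mentioned.

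**Working it through.** There is no figure in the plan to reproduce, so the check is a comparison of text. All mentions of the condition were compared, and vaccine allergy, the other contraindication treated in both 9.c and the lists, was taken as a benchmark.

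| Contraindication | Vaccine risk text (9.c) | Listed criteria | With a time window | Without one |
|---|---|---|---|---|
| Guillain-Barre Syndrome | no time limit | 5.b(6), 5.c(21) | 2 of 2 | 0 of 2 |
| Vaccine allergy | no time limit | 5.b(4), 5.c(7), 5.c(23) | 0 of 3 | 3 of 3 |

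**Step 1: apply the lists.** Take a recruit whose episode was four months ago. Items 5.b(6) and 5.c(21) do not apply. No other item in 5.b to 5.e names the condition. The recruit passes.

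**Step 2: apply the risk text.** Under 9.c the same recruit should not be vaccinated, and under 9.d is to be excluded. The two results conflict, and they conflict equally for an episode ten years ago.

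**Step 3: look for a reason for the window.** Nothing in the document explains a 3-month rule for vaccination. Allergy is handled without a window, for example in 5.c(23): "History of allergic reaction to vaccination". For seizures, 5.c(27) covers both a significant history and the last 3 months. The authors therefore did add past history to a recency window in at least one other case, but not here.

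**Step 4: consider the rule on temporary exclusions.** The opening of section 5 lets recruits join once a temporary criterion no longer applies. It does not say which criteria are temporary. A 3-month item is naturally read as one of them, and it expires by its own terms in any case.

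**Step 5: size.** The documents give no frequency of past Guillain-Barre Syndrome. Purely as an assumption, take 0% to 1%. Section 1.a of the human subjects part plans 200 people consented and screened and 100 participating; section 1.b requests 50 to complete the exercise and supplementation protocol.

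- Screened: 200 × 0 to 0.01 = 0 to 2 people
- Participating: 100 × 0 to 0.01 = 0 to 1 person
- Completing: 50 × 0 to 0.01 = 0 to 0.5 person

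**The case against.** The best case for the plan is that it already handles this. Section 9.d is itself a binding statement, so knowingly vaccinating someone with an older episode would breach the protocol whatever the lists say. The lists are expressly not exhaustive, since 5.d(18) and 5.f call for physician judgment. There are several chances for the history to emerge: with the recruit's permission a physician reviews the CPRS problem list, with no look-back limit stated for that review; a physician takes a medical history and discusses the exclusion criteria; subjects are told the vaccine risks; and a study physician is the planned vaccinator. The Medical History and Physical Exam form is not in the documents, so it cannot be said that it asks about 3 months only.

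It can also be argued that the window is deliberate. It appears identically in two lists, among other recency limits such as 3 months for myocardial infarction and 7 days for encephalopathy. The sentence in 9.c is ungrammatical and could be read as meaning Guillain-Barre Syndrome that followed a vaccination.

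Much of the first argument stands as mitigation: the practical risk is lower than the lists alone suggest. It does not remove the conflict. The judgment clauses are general and do not name the condition, and each safeguard works only if the older history surfaces. A screener who applies the named criteria as written would admit someone whom 9.c and 9.d bar.

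On the second argument, the documents cannot settle which text the authors intended. But even the narrower reading of 9.c carries no 3-month limit, so one of the two texts has to change.

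**Conclusion.** The concern holds. Both criteria that name Guillain-Barre Syndrome are narrower than the exclusion promised in 9.c and 9.d, and no other listed criterion covers an older episode. This rests on the wording alone and needs no outside source.

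The consequence is limited. The number affected is probably very small: 0 to 2 of 200 screened under the assumed 0% to 1%, a range that includes zero and has no basis in the documents. The conclusion does not depend on that count. The documents do not show that anyone would be harmed, and power, type I error and the analyses are untouched. The change is still worth making, because the inconsistency concerns a safety criterion for a procedure planned for every participant.

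**What to change.** Delete the 3-month limit from 5.b(6) and 5.c(21), so that both read *History of Guillain-Barre Syndrome*. This brings the lists into line with 9.c and 9.d and with the way vaccine allergy is already handled. If the Medical History and Physical Exam form carries the 3-month window, change it there too.

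If the study physicians did mean the 3-month rule, state that window in 9.c and give the reason for it, so that 9.d no longer promises a wider exclusion than the lists provide.

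The cost of the main fix is a wording change in two criteria and possibly one form. It may exclude a few more recruits (0 to 2 of 200 on the assumption above), all of whom 9.d already says should be excluded.

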Study Summary (Figure 9): Veterans (age 60-80 yrs, N=50) will participate in a randomized double-blind placebo-controlled trial. The trial will evaluate the effects of a nutritional supplement (Muscle Armor) on immune function, muscle adaptation to resistance training, and retention of exercise benefits after training is halted. Individual participation will last approximately one year (≥ 47 weeks). This time will include periods for screening and introduction to exercise, supplementation prior to training (2 weeks), supplementation plus supervised resistance training (36 sessions), and supplementation during post-training follow-up (26 weeks). Subjects will undergo four muscle biopsies and blood draws to measure the effects of supplementation on the immune response to a bout of exercise. A fifth biopsy will be collected to measure cellular adaptations in muscle to resistance training. Five additional blood draws will occur to assess eligibility, safety, markers of inflammation, and the response to vaccination for tetanus, diphtheria, and pertussis (TDAP). Strength will be measured bi-weekly, mass and function will be measured at baseline, and after the training and post-training/detraining periods.

Figure 9: Approximate timeline of subject participation and summary of trial protocol.

	Week of Participation: 1	2	5	8	9	10	21	37	47
Physical Exam	X								
Intro to Exercise & Function Testing	X	X							
Blinded Randomization	X								
CT Scan			X				X		X
Strength & Function Testing			X				X	X	X
Single Exercise Session			X	X			X		
Blood Draw	X	X/X	X/X	X	X		X		X
Muscle Biopsy		X/X	X/X				X		
Vaccination				X					
Product Consumption (Twice Daily)				1					42
Resistance Training					1		12		
Detraining Period								1	26
Weekly Reminders	1								47

X/X denotes assessment of response to a single bout of exercise by collecting tissue before and after exercise for blood (1 hour) and muscle (72 hours). The above time-frame is optimal though only an approximation because of scheduling issues related to federal holidays, subject availability, etc.

Key procedures to be completed by veterans (age 60-80, N=50):

- o Pre-screening with required waivers and permissions
- o Enrollment screening after written consent and HIPAA
- o Approximately 50-60 research visits over ~1-year
- o Data collection from CPRS problems and medication lists
- o Orange-flavored supplement or placebo consumption mixed in water twice daily (~42 weeks)

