- o High-Intensity Resistance Exercise (38x over >12 weeks)
- o Post-training follow-up (~26 weeks)
- o Blood draw (9x)
- o Muscle biopsy (5x)
- o Gait and balance testing (4x)
- o TDAP Vaccination (1x)
- o Thigh CT Scan (3x)
- o Compensation (~\$1500): \$20 per visit plus bonuses

HUMAN SUBJECT ASPECTS OF THE STUDY

- 1. Recruitment (Target Population):** Veterans of age 60-80 years will be recruited.
 - a. Accruals Requested: brief pre-screening with required waivers (N=8000), sign consent and undergo screening (N=200), participate in study (N=100), complete all aspects of study considering possible dropout (N=40 to 50). These number will encompass all approved recruitment methods.
 - b. Permission is requested for N=50 to complete the exercise and supplementation protocol after consent and screening. If withdrawal or dropout occurs, no additional data will be collected but specimens or data already collected from the subjects will be used unless the subject requests otherwise.
 - c. Recruitment will not target vulnerable populations. Pregnant women and fetuses, prisoners, and children are excluded from research due to both VA policy and by the purpose of the study. Should a subject become incarcerated, he or she will be withdrawn from the study by the investigator. If the incarceration is only temporary, does not interfere with subject's ability to participate, and the event is discovered by the investigators after the fact, the IRB will be consulted as to whether the subject must be withdrawn.
 - d. Other vulnerable populations (economically and educationally disadvantaged persons, employees and students, and homeless persons) will not be targeted for recruitment but are not specifically excluded. An older veteran may respond to recruitment who by coincidence also happens to be a member of one of these other vulnerable populations. These individuals will undergo the same informed consent process and will be afforded the same research protections as any other participant.
 - e. Individuals with diminished cognitive capacity may possibly respond to the recruitment since the study is targeting older (60-80 yrs) adults. However, individuals lacking the cognitive capacity to consent, as judged by a study physician, will be excluded either during the pre-screening or screening phase. The PI will exclude any individuals who appear unable to understand the consent process.
 - f. Male and female veterans are eligible.

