- c. **Unaccustomed Exercise Sessions (2x):** Prior to exercise training, the study will measure the response to single bouts of the training exercises before and after two weeks of nutritional supplementation. The response to exercise will be measured using both muscle and blood. The pre-exercise time points will be prior to exercise, possibly same day or a different day based on scheduling and/or the judgment of the study physician. The post-exercise time points for collection are 72 hrs for muscle and 1 hr for blood. Our studies have previously shown that 72 hrs is a better than 24 hours for measuring the immune variables of interest in muscle [52].

The 1 hr time point for blood collection is based on other studies that have determined the effects of exercise on systemic measures of immune function [11;53].

- d. **Exercise Training Sessions (36x):** The training program plans to have subjects perform supervised exercise at the NLR VA for approximately an hour optimally 3 times per week on non-consecutive days. The program consists of 36 exercise sessions that will optimally take 12-weeks though the total time will likely be longer due to rescheduling based on the needs of the subject or the study team.
- e. The exercise load will be based on how much the subject is capable of lifting one time. After strength testing, subjects will perform exercises at loads ranging from 60% to 80% (e.g. sets at 60, 70, 75, and 80% of capability) of their measured capability to the best of their ability. Strength is retested at approximately every 6th session to account for strength gain in maintaining the work load. On days of testing, the strength test replaces one of the four exercise sets. Strength is also tested twice prior to training, at the final training bout, and twice during the post-training follow-up period.
- f. Training sessions consist of three sets of 10 repetitions for each exercise and a 4th set completed at voluntary failure to complete a repetition. Subjects will rest approximately two minutes between each set and approximately 5 minutes between exercises.
- g. Exercise data will be recorded for each subject on the Exercise Data Form.

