- b. The resting ratio of CD4+ to CD8+ t-cells will increase in the supplement but not in the placebo group. The change between times G and C will be compared between groups.
- c. The change in t-cell subsets after acute exercise will be greater in the supplement than the placebo group. The change between times I and G will be compared to the change between times E and C for both groups.
- d. Resting cytokine levels will decrease in the supplement but not in the placebo group. Change will be compared between groups for blood (times G and C) and muscle (times H and D). *Similar results are predicted for the MuRF and MAFbx atrophy-related transcripts.*
- e. The increase in cytokine levels after acute exercise will be greater in the placebo group than the supplement group. For both groups, change between times I and G will be compared to the change

Table 6. Time points are lettered for clear reference by the stated hypotheses.	
BASELINE MEASURES (WEEKS 1-5)	
A.	Blood draw at study enrollment for measuring pre-vaccination antibody titers
B.	Assessment of muscle strength, mass, and function at baseline
C.	Blood drawn prior to acute exercise at baseline
D.	Muscle biopsy prior to acute exercise at baseline
E.	Blood drawn 1 hr after acute exercise at baseline
F.	Muscle biopsy 72 hrs after acute exercise at baseline
POST-SUPPLEMENT RUN-IN MEASURES (WEEK 8)	
G.	Blood drawn prior to acute exercise after 2-weeks of supplementation
H.	Muscle biopsy prior to acute exercise after 2-weeks of supplementation
I.	Blood drawn 1 hr after acute exercise after 2-weeks of supplementation
J.	Muscle biopsy 72 hrs after acute exercise after 2-weeks of supplementation
MEASURES DURING TRAINING PERIOD (WEEKS 9-20)	
K.	Blood draws at weeks 1 and 2 post-vaccination for measuring antibody response
POST-TRAINING MEASURES (WEEK 21)	
L.	Assessment of muscle strength, mass, and function after completion of training
M.	Muscle biopsy 72 hrs after final exercise bout of training
MEASURES DURING POST-TRAINING FOLLOW-UP (WEEKS 22-4)	
N.	Assessments of strength, mass, and function after 16 and 26 weeks of detraining

between E and C for blood, and for muscle the change between times J and H will be compared to the change between times F and D.

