- a. The amount of strength gained from 12-weeks of training will be greater in the supplement than the placebo group. The change between times L and B will be compared between groups.
- b. The amount of muscle size gained from 12-weeks of training will be greater in the supplement than the placebo group. The change between times L and B will be compared between groups.
- c. The increase in muscle function after 12-weeks of training will be greater in the supplement than the placebo group. The change between times L and B will be compared between groups.
- d. The increase in muscle satellite cells after 12-weeks of training will be greater in the supplement than the placebo group. The change between times M and D will be compared between groups.
- e. The increase in muscle myonuclei after 12-weeks of training will be greater in the supplement than the placebo group. The change between times M and D will be compared between groups.
- f. The increase in muscle fiber size after 12-weeks of training will be greater in the supplement group than the placebo group. The change between times M and D will be compared between groups.

Aim 3 Power: Aim 3 will determine if supplement consumption increases the retention of exercise-derived benefits post-training during 26 weeks of long-term follow-up. The representative response measure for this objective is the strength gain retained during long-term follow-up after exercise training is completed. Lemmer et al observed an average gain in muscle strength of 27% ($P<0.01$) in older men after strength training which is similar the 25% gain presented here in Finding 4 [65]. However, at

31-weeks of post-training follow-up, strength had decreased to be about 9% above pre-training levels. Assuming the same level of variation among our subjects in retention of strength gain as the observed 8% SD for strength gain in Finding 4, then a 0.8 SD effect size would be about 6.4% ($0.8*0.08$), translating to our supplement group retaining strength of 12.4% above pre-training levels. With 20 subjects per group, there will be 80% power to detect a mean shift of 0.8 SD units using a significance level of 5%. If the SD for retention of strength is smaller than 8%, then we will have higher power to detect the same difference or equal power to detect smaller differences for the following Aim 3 hypotheses:

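### Hypothesis 2a compares only time L with time B, so a subject who leaves during training drops out of the Aim 2 strength comparison although interim 1-RM tests are on record

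*Combined protocol and SAP*

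**What the plan says.** **Strength testing.** The Study Summary says: "Strength will be measured bi-weekly". Item 10.e gives the in-training rule: "Strength is retested at approximately every 6th session to account for strength gain in maintaining the work load". It adds the tests outside that rule: "Strength is also tested twice prior to training, at the final training bout, and twice during the post-training follow-up period". Item 10.g covers recording: "Exercise data will be recorded for each subject on the Exercise Data Form".

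**Analysis.** Aim 2 hypothesis a reads: "The amount of strength gained from 12-weeks of training will be greater in the supplement than the placebo group". The contrast follows: "The change between times L and B will be compared between groups". Table 6 defines time L as: "Assessment of muscle strength, mass, and function after completion of training". Its training-period block lists only the post-vaccination blood draws (time K), so the interim strength tests have no analysis time point.

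**Missing data.** The Statistical Plan bases power on a one-sided t-test for independent groups and allows transformations or non-parametric tests for outliers. It names no repeated-measures model, no imputation rule and no analysis population. Item 1.b says that no more data are collected after withdrawal, but that "specimens or data already collected from the subjects will be used unless the subject requests otherwise".

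**The concern.** Strength gain is the measure on which Aim 2 is powered, and it is the one Aim 2 endpoint with serial measurements. At about every 6th of 36 sessions, a subject who leaves after session 30 has roughly five in-training 1-RM results (sessions 6, 12, 18, 24 and 30). None can be used in an L-B change score, because L does not exist for that subject.

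Two things are at stake. One is precision, since recorded information on the outcome goes unused. The other, more important, is that the comparison is restricted to people who finish training and is no longer a comparison of the groups as randomised. If poor early responders leave one arm more often, that arm's completer mean is too high. The planned test is one-sided, so upward bias in the supplement arm raises the chance of a false positive. The interim tests would also show whether leavers were poor responders.

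**Working it through.** **1. The plan's own power.** Inputs from Aim 2 Power: 20 per group, placebo gain 25%, relative improvement 25.1%, SD 8%, 5% level, one-sided.
- Planned difference: 25 × 0.251 = 6.3 points. Effect size: 0.25 × 0.251 / 0.08 = 0.784, rounded in the plan to 0.8.
- Exact one-sided t-test power, 20 per group, 0.8 SD: 79.9%. The stated 80% reproduces.
- The pilot-study section gives N=50 with 20% dropout: 20 / (1 − 0.20) = 25 per arm, assuming equal allocation. The power therefore gives no weight to up to 5 subjects per arm.

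**2. Precision.** Assume all 5 per arm leave during training with at least one interim test, and that loss is ignorable given observed strength. Let r be the correlation between the last interim change and the final change (not in the documents). In units of the outcome variance, each arm mean has

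variance = (1 − r²)/20 + r²/25,

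against 1/20 for completers. The SE ratio is √(1 − 0.2r²).

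| r | Effective n per arm | SE ratio | One-sided power |
|---|---|---|---|
| 0.3 | 20.4 | 0.99 | 80.6% |
| 0.5 | 21.1 | 0.97 | 81.7% |
| 0.7 | 22.2 | 0.95 | 83.4% |
| 0.9 | 23.9 | 0.92 | 85.8% |

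The saving is about 1 to 5% of the SE for r up to 0.7, and 8% at r = 0.9. A simulation of 4, 6 and 10 random losses among 50 (gain SD 15, test error SD 5) gave SE ratios of 0.973, 0.965 and 0.954. The ceiling, with full information on 25 per arm, is 87.4% power.

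**3. Bias under no effect.** Suppose a fraction p leaves one arm only, and the tendency to leave correlates ρ with poor gain. That arm's completer mean shifts by

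SD × ρ × φ(z) / (1 − p), with z the p-quantile of the standard normal.

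ρ is an assumption; 0.35 is used here.

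| Lost from one arm of 25 | p | φ(z)/(1 − p) | Shift at SD 8 | Shift at SD 15 |
|---|---|---|---|---|
| 4 | 0.16 | 0.290 | 0.8 | 1.5 |
| 6 | 0.24 | 0.409 | 1.1 | 2.1 |
| 10 | 0.40 | 0.644 | 1.8 | 3.4 |

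Simulation of this pattern gave about +0.8 to +1.9 points at SD 8, which is 13 to 30% of 6.3 (0.8/6.3 and 1.9/6.3). The result scales with ρ: at ρ = 0.5 the SD 8 column becomes 1.2, 1.6 and 2.6.

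SD 15 is shown because Finding 4 reports gains from +8% to +65% in 8 people. The smallest sample SD compatible with that range puts the other six at the midpoint: √(2 × 28.5² / 7) = 15.2. This applies only if the range and the 25 ± 8% describe the same strength measure.

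**4. What the interim tests recover.**
- Leaving depends on observed early strength: an estimate using the interim tests has bias near zero.
- Leaving depends on true gain in one arm: at SD 8 in one simulation, bias was 1.1 to 2.6 points for completers and 0.8 to 1.9 with all tests. It is reduced, not removed.
- Same selection in both arms, or random loss: completer bias is about zero.

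**The case against.** **No contradiction with item 1.b.** A reader might infer that the plan breaks its own promise to use data from people who withdraw. It does not. Item 1.b is about keeping and using data after withdrawal; it does not define an analysis set for each test. Someone who leaves during training has normally supplied most or all of the Aim 1 data, since times A and C to J precede training and K comes 1 and 2 weeks after vaccination. Such subjects do not contribute nothing to the trial; the gap is in the Aim 2 strength comparison.

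**Completers-only is a consequence, not a statement.** The plan never declares such an analysis. This stands, but an L-B score without a missing-data rule leaves no other reading of how 2a would be computed.

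**The bias needs particular conditions.** Nothing in the documents indicates that loss will differ by arm or relate to strength. The 20% allowance covers at least 47 weeks, so loss within the 36 sessions may be well below 10 of 50. The near-zero bias of the all-tests model also holds by construction when leaving depends on observed strength. All of this stands, and the bias should be read as an exposure, not a forecast.

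**The interim tests exist to set the load.** That is their stated purpose, and an L-B change is a conventional endpoint. But they are 1-RM tests recorded for each subject, so they can serve as outcome data.

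**Conclusion.** The point holds for hypothesis 2a. Anyone lacking time L drops out of the Aim 2 strength comparison, while 1-RM results on that person go unused.

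The precision loss is small, about 1 to 5% of the SE under plausible correlations. The main reason to act is protection against bias: roughly +0.8 to +1.9 points at the plan's SD of 8, and more at SD 15, against a planned 6.3. That rests on assumed selective loss of 4 to 10 subjects from one arm; with random or similar loss in both arms the bias is about zero.

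A reader might also infer that the stated power is wrong. It is not: it reproduces at 79.9% and already counts 20 per group. This is a worthwhile change to the analysis, not a defect in the sample size.

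**What to change.** Specify for hypothesis 2a a likelihood-based repeated-measures model of 1-RM strength at the pre-product baseline, the interim tests and L.
- **Population:** put baseline in the response vector, so that every randomised subject with a baseline is included, even one who leaves before the first retest.
- **Effects:** nominal session block as a category, with arm-by-block effects. The arm contrast at L is the Aim 2 result.
- **Outcome:** name the lift (press, curl or extension) or the composite, and which of the two pre-training tests is the baseline.
- **Covariance:** unstructured, with a prespecified simpler fallback. Baseline, five interim tests and L make 7 occasions, hence 7 × 8 / 2 = 28 parameters from about 50 people.
- **Sensitivity analyses:** the L-B comparison in completers, and an analysis that allows loss to depend on unobserved strength.

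The cost is a paragraph in the Statistical Plan and database entry of values already on the Exercise Data Form. There are no new visits or tests. The model assumes that loss depends on observed strength; otherwise it reduces bias without removing it. Hypotheses 2b to 2f have no interim measures and gain nothing from this change, so they still need their own missing-data rule.
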